10.1.6 Other safety assessments

If new or worsening pulmonary symptoms (e.g., dyspnea) or radiological abnormality suggestive of pneumonitis/ILD is observed, toxicity management as described in detail in the Dosing Modification and Toxicity Management Guidelines (see Appendix 1) will be applied. The results of the full diagnostic workup (including high-resolution computed tomography [HRCT], blood and sputum culture, hematological parameters, etc.) will be captured in the eCRF. It is strongly recommended to perform a full diagnostic workup, to exclude alternative causes such as lymphangitic carcinomatosis, infection, allergy, cardiogenic edema, or pulmonary hemorrhage. In the presence of confirmatory HRCT scans where other causes of respiratory symptoms have been excluded, a diagnosis of pneumonitis (ILD) should be considered and the Dosing Modification and Toxicity Management Guidelines should be followed.

The Principal Investigator is responsible for ensuring that all staff involved in the study is familiar with the content of this section.

10.2 Safety parameters

10.2.1.1 Definition of adverse events

The International Conference on Harmonization (ICH) Guideline for Good Clinical Practice (GCP) E6(R1) defines an AE as:

Any untoward medical occurrence in a patient or clinical investigation patient administered a pharmaceutical product and which does not necessarily have a causal relationship with this treatment. An AE can therefore be any unfavorable and unintended sign (including an abnormal laboratory finding), symptom, or disease temporally associated with the use of a medicinal product, whether or not considered related to the medicinal product.

An AE includes but is not limited to any clinically significant worsening of a patient's pre-existing condition. An abnormal laboratory finding (including ECG finding) that requires an action or intervention by the investigator, or a finding judged by the investigator to represent a change beyond the range of normal physiologic fluctuation, should be reported as an AE.

Adverse events may be treatment emergent (i.e., occurring after initial receipt of investigational product) or nontreatment emergent. A nontreatment-emergent AE is any new sign or symptom, disease, or other untoward medical event that begins after written informed consent has been obtained but before the patient has received investigational product.

Elective treatment or surgery or preplanned treatment or surgery (that was scheduled prior to the patient being enrolled into the study) for a documented pre-existing condition, that did not worsen from baseline, is not considered an AE (serious or nonserious). An untoward medical event occurring during the prescheduled elective procedure or routinely scheduled treatment should be recorded as an AE or SAE.

The term AE is used to include both serious and non-serious AEs.

10.2.2 Definition of serious adverse events

A serious adverse event is an AE occurring during any study phase (i.e., screening, run-in, treatment, wash-out, follow-up), at any dose of the study drugs that fulfils one or more of the following criteria:

- Results in death
- Is immediately life-threatening
- Requires in-patient hospitalization or prolongation of existing hospitalization
- Results in persistent or significant disability or incapacity
- Is a congenital abnormality or birth defect in offspring of the patient
- Is an important medical event that may jeopardize the patient or may require medical intervention to prevent one of the outcomes listed above.
 - Medical or scientific judgment should be exercised in deciding whether expedited reporting is appropriate in this situation. Examples of medically important events are intensive treatment in an emergency room or at home for allergic bronchospasm, blood dyscrasias, or convulsions that do not result in hospitalizations; or development of drug dependency or drug abuse.

Clinical Study Protocol

Investigational Drug Substance: MEDI4736 Sirolimus (Rapamune)

Study Number **19-20015**

Edition Number: 4

Date: **11 February 2022**

The causality of SAEs (their relationship to all study treatment/procedures) will be assessed by the investigator(s) and communicated to AstraZeneca.

10.2.3 Definition of adverse events of special interest (AESI)

An adverse event of special interest (AESI) is one of scientific and medical interest specific to understanding of the Investigational Product and may require close monitoring. An AESI may be serious or non-serious.

If the Investigator has any questions in regards to an event being an imAE, the Investigator should promptly contact the Study Physician.

AESIs observed with durvalumab include:

- Diarrhea / Colitis and intestinal perforation
- Pneumonitis / ILD
- hepatitis / transaminase increases
- Endocrinopathies (i.e. events of hypophysitis/hypopituitarism, adrenal insufficiency, hyper- and hypothyroidism and type I diabetes mellitus)
- Rash / Dermatitis
- Nephritis / Blood creatinine increases
- Pancreatitis / serum lipase and amylase increases
- Myocarditis
- Myositis / Polymyositis

Neuropathy / neuromuscular toxicity (e.g. Guillain-Barré, and myasthenia gravis)

- Other inflammatory responses that are rare / less frequent with a potential immune-mediated aetiology include, but are not limited to, pericarditis, sarcoidosis, uveitis and other events involving the skin of the eyes, haematological and rheumatological events, vasculitis, non-infectious meningitis and non-infectious encephalitis.

In addition, infusion-related reactions and hypersensitivity/anaphylactic reactions with a different underlying pharmacological etiology are also considered AESIs.

Further information on these risks (e.g. presenting symptoms) can be found in the current version of the durvalumab Investigator's Brochure. More specific guidelines for their evaluation and treatment are described in detail in the Dosing Modification and Toxicity Management Guidelines (please see Appendix 1). These guidelines have been prepared by the Sponsor to assist the Investigator in the exercise of his/her clinical judgment in treating these types of toxicities. These guidelines apply to AEs considered causally related to the study drug/study regimen by the reporting investigator.

If new or worsening pulmonary symptoms (e.g. dyspnea) or radiological abnormality suggestive of pneumonitis/interstitial lung disease is observed, toxicity management as described in detail in the Dosing Modification and Toxicity Management Guidelines (see **Error! Reference source not found.**) will be applied. The results of the full diagnostic workup (including high-resolution computed tomography (HRCT), blood and sputum culture, hematological parameters etc.) will be captured in <<specify where this information will be recorded e.g. eCRF, CRF, etc.)>>

It is strongly recommended to perform a full diagnostic workup, to exclude alternative causes such as lymphangitic carcinomatosis, infection, allergy, cardiogenic edema, or pulmonary hemorrhage. In the presence of confirmatory HRCT scans where other causes of respiratory symptoms have been excluded, a diagnosis of pneumonitis (ILD) should be considered and the Dosing Modification and Toxicity Management Guidelines should be followed.

Pneumonitis (ILD) investigation

The following assessments, and additional assessments if required, will be performed to enhance the investigation and diagnosis of potential cases of pneumonitis. The results of the assessment will be collected.

- Physical examination
 - Signs and symptoms (cough, shortness of breath and pyrexia, etc.) including auscultation for lung field will be assessed.
- SpO2
 - Saturation of peripheral oxygen (SpO2)
- Other items
 - When pneumonitis (ILD) is suspected during study treatment, the following markers should be measured where possible:

Clinical Study Protocol

Investigational Drug Substance: MEDI4736 Sirolimus (Rapamune)

Study Number **19-20015**

Edition Number: **4**

Date: **11 February 2022**

- (i) ILD Markers (KL-6, SP-D) and β -D-glucan
- (ii) Tumor markers: Particular tumor markers which are related to disease progression.

Additional Clinical chemistry: CRP, LDH

10.2.4 Safety data to be collected following the final DCO of the study

For patients continuing to receive durvalumab treatment after final DCO and database closure, it is recommended that the patients continue the scheduled site visits and Investigators monitor the patient's safety laboratory results prior to and periodically during treatment with durvalumab in order to manage AEs in accordance with the durvalumab Dose Modification and Toxicity Management Guidelines (see Appendix 1). All data post the final DCO and database closure will be recorded in the patient notes but, with the exception of SAEs, will not otherwise be reported for the purposes of this study.

All SAEs that occur in patients still receiving durvalumab treatment (or within the 90 days following the last dose of durvalumab treatment) post the final DCO and database closure must be reported as detailed in Section 10.5

10.3 Assessment of safety parameters

10.3.1 Assessment of severity

Assessment of severity is one of the responsibilities of the investigator in the evaluation of AEs and SAEs. Severity will be graded according to the NCI CTCAE v5.0.

The determination of severity for all other events not listed in the CTCAE should be made by the investigator based upon medical judgment and the severity categories of Grade 1 to 5 as defined below.

Grade 1 (mild)	An event that is usually transient and may require only minimal treatment or therapeutic intervention. The event does not generally interfere with usual activities of daily living.
Grade 2 (moderate)	An event that is usually alleviated with additional specific therapeutic intervention. The event interferes with usual activities of daily living, causing discomfort but poses no significant or permanent risk of harm to the patient.
Grade 3 (severe)	An event that requires intensive therapeutic intervention. The event interrupts usual activities of daily living, or significantly affects the clinical status of the patient.
Grade 4 (life-threatening)	An event, and/or its immediate sequelae, that is associated with an imminent risk of death or with physical or mental disabilities that affect or limit the ability of the patient to perform activities of daily living (eating, ambulation, toileting, etc.).
Grade 5 (fatal)	Death (loss of life) as a result of an event.

It is important to distinguish between serious criteria and severity of an AE. Severity is a measure of intensity whereas seriousness is defined by the criteria in Section 10.1.2. A Grade 3 AE need not necessarily be considered an SAE. For example, a Grade 3 headache that persists for several hours may not meet the regulatory definition of an SAE and would be considered a non-serious event, whereas a Grade 2 seizure resulting in a hospital admission would be considered an SAE.

10.4 Recording of adverse events and serious adverse events

AEs and SAEs will be collected from the time of the patient signing the informed consent form until the follow-up period is completed (90 days after the last dose of durvalumab). <<teams to include required follow up period for the comparator agent>>). If an event that starts post the defined safety follow up period noted above is considered to be due to a late onset toxicity to study drug then it should be reported as an AE or SAE as applicable.

During the course of the study, all AEs and SAEs should be proactively followed up for each patient for as long as the event is ongoing. Every effort should be made to obtain a resolution for all events, even if the events continue after the patient has discontinued study drug or the study has completed.

Any AEs that are unresolved at the patient's last visit in the study are followed up by the Investigator for as long as medically indicated, but without further recording in the CRF.

AstraZeneca retains the right to request additional information for any patient with ongoing AE(s)/SAE(s) at the end of the study, if judged necessary.

The following variables will be collected for each AE:

In addition, the following variables will be collected for SAEs as applicable:

- AE (verbatim)
- The date when the AE started and stopped
- The maximum CTCAE grade reported
- Changes in CTCAE grade
- Whether the AE is serious or not
- Investigator causality rating against the IPs (yes or no)
- Action taken with regard to IPs
- Administration of treatment for the AE
- Outcome

In addition, the following variables will be collected for SAEs:

- Date the AE met criteria for SAE

Clinical Study Protocol

Investigational Drug Substance: MEDI4736 Sirolimus (Rapamune)

Study Number **19-20015**

Edition Number: 4

Date: **11 February 2022**

- Date the Investigator became aware of the SAE
- Seriousness criteria fulfilled
- Date of hospitalization
- Date of discharge
- Probable cause of death
- Date of death
- Whether an autopsy was performed
- Causality assessment in relation to study procedure(s)
- Causality assessment in relation to other medication, as explained in Section 10.4.2
- Description of the SAE

The grading scales found in the NCI CTCAE version 5.0 will be utilized for all events with an assigned CTCAE grading. For those events without assigned CTCAE grades, the recommendation in the CTCAE criteria that converts mild, moderate, and severe events into CTCAE grades should be used. A copy of the CTCAE version 5.0 can be downloaded from the Cancer Therapy Evaluation Program website (<http://ctep.cancer.gov>).

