Edition Number: **4**

Date: **11 February 2022**

- To evaluate the efficacy of sirolimus followed by durvalumab as neoadjuvant treatment for Stage I, II, and IIIA NSCLC

Secondary Objective(s):

- To evaluate the efficacy of sirolimus followed by durvalumab as neoadjuvant treatment for Stage I, II, and IIIA NSCLC
- To evaluate response to sirolimus followed by durvalumab in patients with PD-L1 positive vs. PD-L1-negative tumors
- To evaluate the association between blood mutation burden and response to sirolimus followed by durvalumab

Exploratory Objective(s):

- To evaluate the immune-mediated effects of sirolimus followed by durvalumab
- To investigate tumor and immune microenvironment changes in tissue samples

Study Design:

Up to 31 patients with NSCLC will be enrolled in this study at Emory University Winship Cancer Institute and associated clinical sites. Eligible patients will complete 3 weeks of daily oral sirolimus followed by 2 cycles of durvalumab treatment prior to proceeding to standard of care surgical resection. Durvalumab will be administered at a dose of 1500mg Q 3 weeks starting on C1D1 for up to 2 cycles that are 21 days in length. Pharmacodynamic analysis will be done using PD samples collected at baseline (tissue) and with blood samples on day 1, day 22 C1 prior to durvalumab, day 43 C2 durvalumab, and at the time of surgery (blood and tissue). Additional post surgery blood samples will be collected at 1-, 3-, and 6-months post-surgery. See Appendix D for schedule of Biomarker collection. Patients will proceed to surgery within a 2–3-week period post 2nd dose of durvalumab but not earlier than two weeks after the administration of durvalumab i.e. not earlier than C2D14. Additionally, as an optional study, patients will self-administer heavy water (D2O) 50ml orally three times a day from day 22 C1 through day 27 followed by 50ml orally twice a day through the day prior to surgery in order to label dividing cells for research tracking purposes.

Number of Centers: Emory University Winship Cancer Institute and affiliated hospitals

Number of Patients: 31

Study Population: Resectable Stage 1-3A NSCLC

Inclusion Criteria:

- Pathologically documented NSCLC who are candidates for surgical resection
- Capable of signing informed consent

- Age \geq 18 years at time of study entry.
- Eastern Cooperative Oncology Group (ECOG) performance status of 0 or 1
- Life expectancy of \geq 26 weeks
- Body weight >30 kg

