A comparison of both the *complete pathologic response* and investigator assessed response rates per RECIST v1.1 rates between the PD-L1 positive and PD-L1 negative groups will be performed by calculating the lower bound of a one-sided 80% CI for the difference, complete pathologic response for PDL-1 positive patients – complete pathologic response for PDL-1 negative patients. Chi-square test or Fisher's exact test will be used to compare the efficacy in term of response rate between the different groups stratified by other factors, respectively. Logistics regression model will be further employed to test the adjusted effect of each other factor on the response rate after adjusting for other clinical factors and demographic factors, respectively. Correlation of response will be performed for tumor mutation burden using spearman correlation coefficient and tested with Wald's test.

Sample Size Determination:

Pathologic complete response is rare following neoadjuvant chemotherapy but was reported in 0-8% of cases³⁹. The current study is designed to test improved rate of pathologic complete response from 10% to 25% with sequential treatment with sirolimus and durvalumab. Using a MinMax 2-stage design, a total of 31 patients will be enrolled in 2 stages. At the end of stage I, at least 2 of 16 patients must achieve complete pathologic complete response in order for the study to enroll 15 additional patients. The regimen of sirolimus followed by durvalumab will be considered to have sufficient efficacy to warrant further testing in this patient population if 6 or more of the 31 patients achieve a pathologic CR at the end of stage II. The study has 80% power at a 1-sided alpha of 0.1 to show a compelling 25% pCR compared to a less compelling rate of 10%. Because this is a signal finding study, an alpha of 0.1 is considered reasonable since any promising signal will be confirmed in a larger follow-up study.

Clinical Study Protocol

Drug Substance Sirolimus (Rapamune)

Study Number **19-20015**

Edition Number: **4**

Date: **11 February 2022**

SCHEDULE OF STUDY ASSESSMENTS

	Screening	Sirolimus	Durvalumab C1	Durvalumab C2	Pre- surgery	Surgery	Study DC	Follow- up	For details see Section				
Week	-4 to 0	0	3	6	8-9		Post Surgery 30 +/- 7 days	Every 3 months for 2 years					
Day	-28 to 0	1-21	22 +/- 3 days^a	43 +/- 3 days^a	57-64 +/- 10 days								
Informed Consent													

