3. STUDY DESIGN

3.1 Overview of study design

This is a Phase Ib open-label, single-arm study in newly diagnosed stage I-IIIA NSCLC patients, to test sirolimus in combination with durvalumab as neoadjuvant treatment prior to curative-intent surgical resection. The safety and tolerability as well as efficacy of combination sirolimus with durvalumab will be evaluated in this treatment setting. The study is also designed to investigate a number of laboratory correlative studies to define mechanisms of anti-tumor activity of sirolimus + durvalumab and several potential predictive biomarkers, which will help identify patients who are more likely to respond to treatment. Finally, the study will also include DFS and OS as secondary endpoints.

Up to 31 patients with NSCLC will be enrolled in this study at Emory University Winship Cancer Institute and affiliated sites. Enrollment will occur in 2 parts based on Simon 2 stage design, in which at least 2 of the first 16 patients must achieve pathologic complete response in order for the study to enroll 15 additional patients.

Eligible patients will complete 2 cycles of outpatient study treatment prior to proceeding to standard of care surgical resection. In order to allow a reliable assessment of the contribution of sirolimus versus durvalumab to the observed clinical and PD outcome, treatment will start with sirolimus 6mg orally for one loading dose followed by 2mg orally once daily three weeks prior to the start of durvalumab. Durvalumab will be administered at a dose of 1500mg Q 3 weeks starting on C1D1 for up to 2 cycles that are 21 days in length. Pharmacodynamic analysis will be done using PD samples collected at baseline (tissue) and with blood samples on day -7, C1D1 prior to durvalumab, C1D8, C2D1, C2D8 and at the time of surgery (blood and tissue). Additional post surgery blood samples will be collected at 1, 3, and 6 months post-surgery. See **study schedule of assessments** for schedule of Biomarker collection. Patients will proceed to surgery within a 4-week period post 2nd dose of durvalumab but not earlier than one week after the administration of durvalumab i.e. not earlier than C2D8. Additionally, patients will self-administer heavy water (D2O) 50ml orally three times a day from C1D1 through C1D5 followed by 50ml orally twice a day through the day prior to surgery in order to label dividing cells for research tracking purposes.

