7.2.1 Permitted concomitant medications

Table 4. Permitted Supportive Medications

Supportive medication/class of drug:	Usage:
Concomitant medications or treatments (e.g., acetaminophen or diphenhydramine) deemed necessary to provide adequate prophylactic or supportive care, except for those medications identified as “prohibited,” as listed above	To be administered as prescribed by the Investigator
Best supportive care (including antibiotics, nutritional support, correction of metabolic disorders, optimal symptom control, and pain management [including palliative radiotherapy to non-target lesions, etc.])	Should be used, when necessary, for all patients
Inactivated viruses, such as those in the influenza vaccine	Permitted
Inhaled steroids for COPD, mineralocorticoids (eg fludrocortisone for adrenocortical insufficiency), and prednisone < 10mg daily	Permitted

Clinical Study Protocol

Investigational Drug Substance: MEDI4736 Sirolimus (Rapamune)

Study Number **19-20015**

Edition Number: 4

Date: **11 February 2022**

Standard-of-Care Chemotherapy (with or without Radiation) after Surgical Resection

After surgical resection of their tumor, patients may receive SOC chemotherapy (with or without radiation) after surgical resection of their tumor. Choice of SOC adjuvant therapy will be at the discretion of the treating physician, depending on the stage of their disease, as deemed clinically appropriate.

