8.1.2 Treatment phase

Procedures to be conducted during the treatment phase of the study are presented in the Schedule of Assessments. Screening procedures performed within 72 hours of cycle 1 day 1 do not need to be repeated on cycle 1 day 1.

1. Sirolimus dosing: will be given 6mg po once on day 1, followed by 2mg po daily on days 2-21. Steady state trough levels will be collected on day 23 and stored for batch analysis.
2. Heavy water dosing: first dose to be taken in clinic on day 23 and a 6 week supply for self- administration will be dispensed in labeled conical tubes. The patients will also be shown how to collect salivate samples.
3. Durvalumab dosing: starting on Day 22 q 3 weeks for 2 doses
4. Restaging imaging prior to surgery
5. Standard of care surgical resection
6. Peripheral blood research tube collection per study calendar

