10.5 Reporting of serious adverse events

All SAEs will be reported, whether or not considered causally related to the investigational product, or to the study procedure(s). The reporting period for SAEs is the period immediately following the time that written informed consent is obtained through 90 days after the last dose of durvalumab or until the initiation of alternative anticancer therapy. The investigator and/or Sponsor are responsible for informing the Ethics Committee and/or the Regulatory Authority of the SAE as per local requirements.

All serious, related and unexpected adverse events must be reported to AstraZeneca regardless of the country where the study is conducted.

For those events requiring expedited reporting to the regulatory authorities, the investigator and/or sponsor must inform all applicable regulatory authorities (e.g. FDA), via a MedWatch/AdEERs or applicable required regulatory form (e.g. CIOMS), of any serious, related and unexpected adverse events in accordance with reporting obligations (e.g. FDA21 CFR 312.32) and will concurrently forward all such reports to AstraZeneca in English. A copy of the MedWatch/AdEERs report must be emailed to AstraZeneca at the time the event is reported to the regulatory authorities (e.g. FDA). It is the responsibility of the sponsor to compile all necessary information and ensure that the regulatory authorities receive a report according with the applicable reporting requirement timelines and to ensure that these reports are also submitted to AstraZeneca at the same time.

* A *cover page* should accompany the **MedWatch/AdEERs** form indicating the following:

- “Notification from an Investigator Sponsored Study”
- The investigator IND number assigned by the FDA
- The investigator’s name and address
- The trial name/title and AstraZeneca ISS reference number (ESR-19-20015)

* Sponsor must also indicate, either in the SAE report or the cover page, the *causality* of events *in relation to all study medications* and if the SAE is *related to disease progression*, as determined by the principal investigator.

* ***Send SAE report and accompanying cover page by way of email to AstraZeneca’s designated mailbox:*** [contact]

If a non-serious AE becomes serious, this and other relevant follow-up information must also be provided to AstraZeneca and the FDA.

Clinical Study Protocol

Investigational Drug Substance: MEDI4736 Sirolimus (Rapamune)

Study Number **19-20015**

Edition Number: 4

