Appendix 2: End of Study and Follow-up Evaluations

	Day (+/-7)	Every 3 Months (±4 weeks)			Chart follow-up
		30	3	6	
Full Physical examination	X				
Vital signs (temperature, respiratory rate, blood pressure, pulse)	X				
Weight	X				
Urine hCG or serum βhCG					
AE/SAE assessment	X				
Concomitant medications	X				
Post-operative chemotherapy and/or radiotherapy as clinically indicated		→			
ECOG performance status	X	X	X		
Subsequent anticancer therapy		X	X		
Survival status: phone contact with patients who agree to be contacted and chart review		X	X	X (every 6 months)	
Hematology	X				
Serum chemistry	X				
Research blood collection	X	X	X		
Tumor assessment (CT or MRI) per standard of care		→			

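### AEs and SAEs are to be collected for 90 days after the last durvalumab dose, but Appendix 2 schedules its last AE/SAE assessment about 30 to 65 days after it, and Section 10.5 has an earlier SAE stop that Section 10.4 lacks

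*Combined protocol and SAP*

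**What the plan says.** - **Collection rule.** Section 10.4 collects AEs and SAEs from consent "until the follow-up period is completed (90 days after the last dose of durvalumab". An event starting later is still reportable if judged a late-onset toxicity of study drug. The same passage contains an unfilled template prompt about follow-up for a comparator.
- **Visit grid.** In Appendix 2 the row "AE/SAE assessment" has one mark, at day 30 (± 7). The 3- and 6-month contacts (± 4 weeks) and the chart follow-up have none. The main schedule places the Study DC visit at "Post Surgery 30 +/- 7 days" and shows AE/SAE assessment as an arrow.
- **SAE reporting rule.** Section 10.5 runs "through 90 days after the last dose of durvalumab or until the initiation of alternative anticancer therapy". Section 10.4 has no such second stop.
- **Treatment after surgery.** Section 7.2.1: "After surgical resection of their tumor, patients may receive SOC chemotherapy (with or without radiation"), with the choice depending on stage.
- **Timing of the last dose and surgery.** Section 8.1.2: "Durvalumab dosing: starting on Day 22 q 3 weeks for 2 doses". The synopsis places surgery "within a 2–3-week period post 2nd dose of durvalumab but not earlier than two weeks after the administration of durvalumab"; Section 3.1 says "surgery within a 4-week period post 2nd dose of durvalumab but not earlier than one week after the administration of durvalumab".
- **Use of the data.** Section 2.1 makes AE incidence and severity a co-primary objective. Section 11.2.1 reports the number and percentage of patients with AEs.

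**The concern.** The plan treats 90 days after the last durvalumab dose as the relevant safety period, but the visits it schedules do not appear to cover that period. Between the post-surgery visit and day 90, an event reaches the database only if the patient volunteers it or someone happens to notice it. A percentage of patients with AEs would naturally be read as a 90-day incidence, although scheduled enquiry ended earlier and on a different day for each patient.

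The two end rules add to this. A site following Section 10.5 could stop SAE reporting when adjuvant treatment begins, while a site following Section 10.4 would continue to day 90. Adjuvant treatment depends on stage, so the length of SAE observation could differ by stage. For scale only: with 31 patients, one patient is 1/31 = 3.2 percentage points of a co-primary incidence.

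**Working it through.** This is calendar arithmetic; no sample-size formula is involved.

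**Reproducing the plan's own dates.** Dose 1 is on day 22 and dose 2 is 21 days later: 22 + 21 = day 43. The synopsis window of 14-21 days gives surgery on day 43 + 14 = 57 to 43 + 21 = 64, which matches the pre-surgery column of the main schedule (day 57-64).

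**Last scheduled AE/SAE assessment, in days after dose 2.** The visit is 30 ± 7, so 23 to 37, days after surgery. Earliest = earliest surgery + 23; latest = latest surgery + 37. Days with no scheduled enquiry = 90 minus the visit day.

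| Surgery window | Surgery, days after dose 2 | Last AE/SAE assessment | Unscheduled part of the 90 days |
|---|---|---|---|
| Synopsis | 14-21 | 14 + 23 = 37 to 21 + 37 = 58 | 90 − 58 = 32 to 90 − 37 = 53 |
| Section 3.1 | 7-28 | 7 + 23 = 30 to 28 + 37 = 65 | 90 − 65 = 25 to 90 − 30 = 60 |
| Main schedule, day 57-64 ± 10 read as the surgery date | 47 − 43 = 4 to 74 − 43 = 31 | 4 + 23 = 27 to 31 + 37 = 68 | 90 − 68 = 22 to 90 − 27 = 63 |

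Under Section 3.1 the gap is 25/90 = 28% to 60/90 = 67% of the window.

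**Could the visit still reach day 90?** Surgery would have to fall 90 − 37 = 53 to 90 − 23 = 67 days after the last dose, outside every stated window. Section 8.1.3 can be read as counting the visit from hospital discharge, which adds the length of stay. Even the latest Section 3.1 case would need a stay of 90 − 65 = 25 days. The documents give no expected stay.

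**Patients with one dose only** (day 22, surgery on day 57-64): 57 − 22 + 23 = 58 to 64 − 22 + 37 = 79 days. With the ± 10-day tolerance this is 47 − 22 + 23 = 48 to 74 − 22 + 37 = 89, still short of 90.

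**Where the 3-month contact falls** (assuming it is timed from surgery, and 3 months = 91 days):
- Synopsis window: nominally 14 + 91 = 105 to 21 + 91 = 112 days after dose 2; with ± 28 days, 77 to 140.
- Section 3.1 window: nominally 7 + 91 = 98 to 28 + 91 = 119; with ± 28 days, 70 to 147.

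The nominal contact is always after day 90, but an early one can fall before it.

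**The case against.** The strongest reply is that the collection rule, not the visit grid, governs, and that other routes exist:
- Section 10.4 sets 90 days whatever the grid shows and adds the late-onset clause.
- Section 10.4.4 takes spontaneous reports, observation and an open question covering the time since the patient was last asked.
- Section 10.1.5 makes a significant ECOG change reportable as an AE, and Appendix 2 records ECOG at 3 and 6 months.
- Section 10.4.1 captures related SAEs until confirmed progression in patients who discontinue treatment and still have tumor assessments.
- The end of the AE arrow in the main schedule is not legible in the available text. If it runs into follow-up, the fault is a conflict between that table and Appendix 2.
- Section 10.5 governs reporting to the company, ethics committees and regulators, so its earlier stop need not shorten what Section 10.4 records. The protocol does not say whether standard adjuvant therapy counts as alternative anticancer therapy.
- The study is single-arm and AE summaries are descriptive, so unequal observation cannot bias a comparison between arms.

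Much of this stands. A reader might infer that late immune events are under-counted, or are missed selectively in higher-stage patients. The documents support neither statement: they give no late-event rate, no capture rate and no start date for adjuvant therapy, and the stage link rests on one reading of an undefined term.

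The mismatch itself remains. The look-back question is not scheduled at month 3, the concomitant-medication row in Appendix 2 also ends at day 30, and the ECOG rule captures only events that change performance status. The late-onset clause concerns events starting after the window and schedules no enquiry inside it.

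**Conclusion.** The concern holds as a mismatch between the stated window and the scheduled assessments. Under Appendix 2, about 25-60 of the 90 days (32-53 under the synopsis surgery window) have no AE enquiry scheduled, and no stated surgery window brings the last assessment to day 90. Separately, Sections 10.4 and 10.5 end at different points; SAE reporting could end earlier in patients given adjuvant therapy if that counts as alternative anticancer therapy.

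The consequence is a risk that late events are missed in the co-primary AE incidence. An actual under-count, or one that differs by stage, is not shown, and its size cannot be computed. The DLT rate and the rule based on the first six patients are unaffected, because the DLT window in Section 6.3 ends at hospital discharge.

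The figures assume dose 2 on day 43 and a visit counted from surgery; counting from discharge moves them somewhat later. The synopsis and Section 3.1 surgery windows contradict each other and must be reconciled. The gap exists under either.

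**What to change.** 1. Reconcile Section 10.4, Section 10.5, the main schedule and Appendix 2 to one AE/SAE end, 90 days after the last durvalumab dose, that does not stop at adjuvant therapy. Remove the template prompt from Section 10.4.
2. Add an AE/SAE enquiry to the existing 3-month contact, looking back to the day-30 visit and made on or after day 90 from the last durvalumab dose. Under the synopsis window the contact could then be at most 105 − 90 = 15 to 112 − 90 = 22 days early, instead of 28. With the earliest Section 3.1 surgery the limit is 98 − 90 = 8 days. Section 3.1 describes recurrence and survival information every 6 months, so it should be aligned with the 3-month contact.
3. Appendix 2 already records subsequent anticancer therapy at months 3 and 6. Capture its start date and tabulate AEs before and after adjuvant therapy, so that events under chemotherapy or radiation can be seen separately.

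The cost is a small data-entry load, a slightly tighter visit window and possibly higher AE counts. No new visit is needed and no treatment changes.
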